9.1.2 Sensitivity and Supplementary Analyses of the Primary Efficacy Endpoint (Estimand 1)

The following sensitivity analyses will be conducted for the robustness of the primary analysis of the primary efficacy endpoint:

- Sensitivity Analysis 1: MI using a copy reference (CR) approach under MNAR assumption (dichotomous endpoints will be calculated from the underlying imputed variable);
- Sensitivity Analysis 2: “Non-responder” analysis;
- Sensitivity Analysis 3: Tipping Point analysis;
- Sensitivity Analysis 4: the primary analysis at Week 12 as per section 9.1.1 will be repeated in the ITT Set using weekly averages of WI NRS obtained by averaging at least 3 daily scores over 7-day periods. No period extension at baseline and week 12 applies for these weekly averages. MI under MAR will be repeated using the weekly averages obtained by averaging at least 3 daily scores over 7-day periods;
- Sensitivity Analysis 5: the primary analysis at Week 12 as per section 9.1.1 will be repeated in the ITT Set using weekly averages of WI NRS obtained by averaging at least 2 daily scores over 7-day periods. No period extension at baseline and week 12 applies for these weekly averages. MI under MAR will be repeated using the weekly averages obtained by averaging at least 2 daily scores over 7-day periods;
- Sensitivity Analysis 6: the primary analysis at Week 12 as per section 9.1.1 will be repeated in the ITT Set using weekly averages of WI NRS obtained by averaging at

least 1 daily score over 7-day periods. No period extension at baseline and week 12 applies for these weekly averages. MI under MAR will be repeated using the weekly averages obtained by averaging at least 1 daily scores over 7-day periods.

See [Appendix C](#) for details about Multiple Imputation and Tipping Point analysis.

The primary analysis imputes all missing data using MI under MAR assumption. The sensitivity analyses and tipping point will investigate the robustness of results to assumptions made for missing data.

In all these sensitivity analyses, subjects who took rescue therapies or discontinued treatment due to lack of efficacy or AE/death related to study drug are considered as treatment failure as defined for this estimand (i.e., the values of the variable of interest collected after the intake of rescue therapies or treatment discontinuation due to lack of efficacy or AE/death related to study drug will be set to the worst possible value and subject's binary response will be imputed as "Non-responder").

In addition, the following supplementary analyses will be conducted:

- Supplementary Analysis 1: the primary analysis at Week 12 as per section [9.1.1](#) will be repeated in the mITT Set; subjects who took rescue therapies or discontinued treatment due to lack of efficacy or AE/death related to study drug are considered as treatment failure as defined for this estimand; MI will not be repeated on the mITT Set and missing values will be imputed using the values of MI under MAR assumption on the ITT Set (dichotomous endpoints will be calculated from the underlying imputed variable);
- Supplementary Analysis 2: the primary analysis at Week 12 as per section [9.1.1](#) will be repeated in the PP Set; subjects who took rescue therapies are considered as treatment failure as defined for this estimand; subjects who discontinued treatment for any reason will not be included in the PP set; subjects with missing data at Baseline or Week 12 will not be included in the PP set and thus no imputation of missing data is needed;
- Supplementary Analysis 3 (Treatment Policy Adaptation): the primary analysis at Week 12 as per section [9.1.1](#) will be repeated in the ITT Set using observed cases only, without any imputation of missing data and without considering either rescue therapies or treatment discontinuation.

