4.2 Sample Size

The sample size calculation is planned to enroll enough subjects to enable the detection of treatment difference in the primary endpoint at Week 12. Approximately 84 subjects will be randomized in each nemolizumab group and in the placebo group for a total sample size of approximately 252 subjects.

Eighty-four (84) subjects per treatment group will have power $\geq 90\%$ to detect difference between placebo group (expected success proportion 20%) and nemolizumab group (30 mg or 60 mg, expected success proportion 50%) at the overall two-sided alpha of 0.05. A two-sided alpha of 0.025 will be spent for the comparison of each nemolizumab dose group versus placebo group.

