4.3 Randomization, Stratification, and Blinding

Subjects will be centrally randomized using an Interactive Response Technology (IRT) system. Allocation concealment will be ensured, as the system will assign the randomization number only upon confirmation of eligibility for a given subject to participate in the study.

Subjects will be randomized in a 1:1:1 ratio to:

- Group 1: 30 mg Nemolizumab Q4W with 60 mg loading dose at baseline;
- Group 2: 60 mg Nemolizumab Q4W without loading dose at baseline;
- Group 3: Placebo Q4W.

Randomization will be stratified by clinical site.

The randomization code will remain blinded to all study sites and study team members until completion of the study and after the study database has been locked.

The IDMC will review data at periodic intervals throughout the study as defined in the IDMC charter. The IDMC charter will specify the procedures for unblinding to ensure that treatment assignment remains undisclosed to all individuals involved in the direct execution and management of the study until the final database is locked.

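### Supplementary Analysis 3 applies treatment policy to rescue and discontinuation but leaves out randomised subjects with a missing baseline or Week 12 average

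*SAP*

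**What the plan says.** The primary analysis (SAP 9.1.1) treats rescue, and discontinuation for lack of efficacy or drug-related AE or death, as non-response. On what is then still missing, SAP 9.1.2 states: "The primary analysis imputes all missing data using MI under MAR assumption".

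Supplementary Analysis 3, in the same section, carries a treatment-policy label. The Week 12 analysis is repeated in the ITT Set "using observed cases only, without any imputation of missing data and without considering either rescue therapies or treatment discontinuation".

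Four other places bear on this:
- SAP 4.11.1 defines the ITT Set as all randomised subjects.
- SAP 9 sets the Week 12 average to missing when fewer than four daily scores are found even after the window is extended. It also says that observed-case summaries keep data collected after rescue or discontinuation.
- SAP 9.1.2 keeps the composite rule in all six sensitivity analyses, which include copy reference, non-responder and tipping point.
- Protocol 19.9 plans the same item simply as an observed case analysis. The treatment-policy label appears only in the SAP.

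**The concern.** A treatment-policy effect in the ITT population concerns every randomised subject. An analysis that names that population but uses only subjects with a Week 12 score answers the question for a subset, and the subset is formed after randomisation. Some of those lost may be subjects the primary analysis counts as failures. Someone who stops for lack of efficacy and also stops the diary is a non-responder in the primary analysis and absent from this one.

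A second difficulty is interpretation. The natural use of Supplementary Analysis 3 is to show how much of the primary result comes from counting rescue and certain discontinuations as failure. Relative to the primary analysis it changes that rule and also switches off imputation. No planned inferential analysis changes the first alone, so a gap between the two results cannot be cleanly attributed to the composite rule.

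**Working it through.** **Inputs.** From SAP 4.2 and 4.3: 84 per arm, 1:1:1 allocation, expected response 20% on placebo and 50% on either dose. On alpha: "A two-sided alpha of 0.025 will be spent for the comparison of each nemolizumab dose group versus placebo group". The documents state neither the share missing at Week 12 nor how missing subjects would have responded, so both are assumptions below. Baseline averages should seldom be missing, because inclusion criterion 5 requires four daily WI NRS scores in the seven days before baseline.

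**The plan's own figure.** Power = Φ[(0.30 − 2.2414·SE0)/SE1], with SE0 = √(2·0.35·0.65/84) = 0.0736 and SE1 = √((0.20·0.80 + 0.50·0.50)/84) = 0.0699. This gives 97.3%, consistent with the stated 90% or more.

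**Who counts, and how.**

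| Subject | Primary analysis | Supplementary Analysis 3 |
|---|---|---|
| Rescue, or stopped for lack of efficacy or drug-related AE; Week 12 present | Non-responder | Observed score |
| Same events or drug-related death; Week 12 missing | Non-responder | Excluded |
| Stopped for another reason; Week 12 present | Observed score | Observed score |
| No composite event; Week 12 missing | Imputed | Excluded |

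The first row is the contrast of interest. The second and fourth rows are altered by the missing-data rule as well.

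**Effect on the estimate.** Let p be the true treatment-policy response rate in an arm, m the share missing, and r the response rate among the missing. The observed-case rate is (p − m·r)/(1 − m). With p = 0.50 and 0.20 and equal m in both arms:

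| Missing subjects | m = 5% | m = 10% | m = 20% |
|---|---|---|---|
| Respond like the observed in their arm | 30.0 | 30.0 | 30.0 |
| Respond at half their arm's rate | 30.8 | 31.7 | 33.8 |
| All non-responders | 31.6 | 33.3 | 37.5 |

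(Differences in percentage points.) Example, half rate at 10%: (0.50 − 0.10·0.25)/0.90 − (0.20 − 0.10·0.10)/0.90 = 0.528 − 0.211 = 0.317.

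With all missing subjects non-responders and unequal missingness:
- 20% active and 10% placebo: 0.625 − 0.222 = 40.3 points.
- 10% active and 20% placebo: 0.556 − 0.250 = 30.6 points.

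**Under no effect.** Take 20% true response in both arms, all missing subjects non-responders, and 20% active against 5% placebo missing. The observed rates are 0.20/0.80 = 25.0% and 0.20/0.95 = 21.1%, a spurious difference of about 4.0 points. The nominal 2.5% test rejects about 5.0% of the time. With 20% against 10% missing, the figures are 2.8 points and about 3.7%.

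**Precision.** For a 30-point difference, 10% missing leaves 84·0.90 = 75.6 per arm and 95.7% power; 20% leaves 67.2 and 93.0%. Loss of power is not the issue.

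**The case against.** The other side has a good deal of substance.

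- **A reader might infer that this is a completer analysis.** The documents do not support that. Subjects who take rescue or stop treatment remain in it whenever they have Week 12 scores, and Protocol 11.5 and 13.2.1 ask them to stay in the study. The completer-type analysis is Supplementary Analysis 2 in the PP Set.
- **A reader might infer that it does not estimate treatment policy at all.** That goes too far. Treatment policy governs intercurrent events, and these are handled as that strategy requires. Missing data are a separate matter of estimation, and the estimate is unbiased if missingness is unrelated to outcome within arm and center.
- **A reader might take it as the only look at the effect regardless of rescue.** Among inferential primary-endpoint comparisons it is. SAP 9 also plans descriptive observed-case summaries that keep post-rescue data.
- **A reader might conclude that nothing separates the two changes.** SAP 9.1.1 plans an unimputed summary of the primary endpoint with rescue counted as failure, which is a partial bridge. It is descriptive and inexact, since a rescued subject without a Week 12 score fails in one and vanishes from the other.
- **The method is disclosed.** The text and the Appendix F table title both say observed case.
- **MI under MAR would not cure the worst case.** If missing subjects are non-responders in a way their earlier scores do not predict, imputation within arm reproduces much of the same bias.

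These arguments limit the severity. They leave two facts in place: the analysed set is not the ITT Set, and no imputed treatment-policy comparison is visible in the plan.

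**Conclusion.** The point holds as a minor one. Supplementary Analysis 3 handles rescue and discontinuation by treatment policy, but it excludes randomised subjects with a missing baseline or Week 12 average. It therefore estimates the treatment-policy effect only under outcome-unrelated missingness, and it cannot cleanly isolate the influence of the composite rule.

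Under the SAP's 50% and 20%, with an assumed 10-20% missing in each arm, the distortion runs from none, through 1.7-3.8 points at half-rate response, to 3.3-7.5 points if no missing subject responds. The top of that range is a worst case and should not be read as the expected bias. The missing rates and the response among the missing are illustrations only.

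The analysis is supplementary and carries no alpha, and the primary MI analysis on the ITT Set is unaffected. Appendix C is redacted, but the statement in 9.1.2 that nothing is imputed stands on its own. The visible text does not say how deaths count here; without a Week 12 score they would drop out.

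**What to change.** Run Supplementary Analysis 3 on the full ITT Set with scores after rescue or discontinuation used as observed and no worst-value substitution. Impute only the missing weekly averages with the same MI under MAR, and state how deaths count. It would then differ from the primary analysis in the intercurrent-event rule, with the same imputation method in both, and would use earlier diary scores that the observed-case analysis discards.

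Keep the observed-case analysis as a separate item under that name, with the number excluded in each arm.

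The cost is one more MI run and one more table. Sensitivity Analyses 4 to 6 already repeat the MI three times, and subjects are already asked to remain in follow-up after rescue or discontinuation. MAR imputation reduces bias only as far as earlier scores predict the missing outcome, and the report should say so.

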9.1.3 Impact of COVID-19 on the Primary Efficacy Endpoint (Estimand 1)

To assess the impact of COVID-19 related study disruptions (e.g. treatment discontinuation, missing assessments, etc.), the primary efficacy endpoint will also be analyzed on the ITT Set excluding subjects affected by COVID-19 related study disruptions. Missing values will be imputed using MI under MAR assumption (dichotomous endpoints will be calculated from the underlying imputed variable). Subjects affected by COVID-19 related study disruptions will not be included in the MI.

9.1.4 Subgroup Analysis for Primary Efficacy Endpoint (Estimand 1)

A summary based on the primary efficacy endpoint (without imputation of missing data) will be repeated in the subgroups defined in section 4.9.

The primary analysis for the primary efficacy endpoint will be repeated in the subgroups defined in section 4.9. The strata-adjusted difference in proportions of responders with 97.5% CI, pooled CMH test p-value will be derived as described in section 9.1.1.

MI will not be repeated on each subgroup and missing values will be imputed using the values of MI under MAR assumption on the ITT Set (dichotomous endpoints will be calculated from the underlying imputed variable).

A Forest plot with the result of primary analysis and all subgroup analysis of primary efficacy endpoint will be presented.

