4 STUDY PERSONNEL

5 SYNOPSIS

[figure not shown]
Title of Study:	A Multicenter, Double-blind, Randomized, Placebo-controlled Study to Evaluate the Efficacy and Safety of Nemolizumab in Subjects with Chronic Kidney Disease with Associated Moderate to Severe Pruritus
Protocol Number:	RD.06.SPR.204358
Investigators/Study Sites:	Approximately 70 study sites are planned in North America and Europe
Phase of Development:	Phase 2/3
Objectives:	
Primary objective: The primary objective is to evaluate the efficacy of nemolizumab compared to placebo at reducing the intensity of pruritus after a 12-week treatment period in adult hemodialysis subjects with moderate to severe pruritus.
 
Secondary objectives: The secondary objectives are to evaluate the safety of nemolizumab compared to placebo, and to assess the CCI [REDACTED] and optimal dose in adult hemodialysis subjects with moderate to severe pruritus.

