4.5 Analysis Centers

Prior to database lock, a review of the blinded data will be performed to determine the size of each center. If there are centers with a small number of randomized subjects, then these centers will be pooled in order for analyses to be carried out. The process of combining centers will be based on the ITT Set, and same pooling will be repeated for the mITT Set and the PP Set.

[figure not shown]
A small center is defined as a center which randomizes less than 15 subjects. First, centers will be sorted by geographic region, country, number of randomized subjects (descending order) and center number (ascending order). Pooling will start with combining the largest of the set of small centers of a country with the smallest center within the same country (if applicable) or within the same geographic region. If there is a further need to combine data (the size of the pooled centers includes less than 15

subjects), the next smallest center will be combined with the next largest of the small centers, until the criterion of a minimum of 15 subjects is met. The process will continue until all pooled centers have a minimum of 15 subjects within the same geographic region. Any remaining small centers of a country/geographic region will be pooled with the last pooled center within the same country/geographic region. The pooled centers and the remaining original unpooled clinical centers will be referred to as ‘analysis centers’ and will be used as stratification factor in the statistical analyses.

If at the start of pooling any geographic region has less than 15 subjects in the ITT Set in total, then centers will be added to the list of small centers in another geographic region and then combined as above. This decision will be documented in Clinical Study Report.

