9.1.1 Primary Analysis of the Primary Efficacy Endpoint (Estimand 1)

A summary will be provided for the primary efficacy endpoint without any imputation of missing data. Note that subjects who took rescue therapies at any point up to and including Week 12 are considered as treatment failures in this endpoint.

In the main statistical analysis described below, missing WI NRS weekly average values will be imputed for the ITT set using multiple imputations (MI) under missing at random (MAR) assumption. Worst values are assumed after use of rescue therapy or treatment discontinuation due to lack of efficacy or AE/death related to study drug prior to imputation. Dichotomous endpoints will be calculated from the underlying imputed variable. See [Appendix C](#) for details about Multiple Imputation.

The proportion of subjects with an improvement at Week 12 of WI NRS ≥ 4 from baseline without use of rescue therapies and without treatment discontinuation due to lack of efficacy or AE/death related to study drug will be analyzed in the ITT Set for each multiply imputed dataset, using the Cochran-Mantel-Haenszel (CMH) test stratified by analysis center; strata-adjusted difference in proportions between treatment groups (Nemolizumab – Placebo) and the 97.5% confidence interval (CI) of the difference will be based on the large sample approximation method for binary data using Mantel-Haenszel strata weights⁸ and the Sato variance estimator⁹. This analysis will be performed for both dosing schedules compared to placebo using the “Commonriskdiff” and “CL=MH” options in SAS PROC FREQ. Proportions and strata-adjusted difference in proportions will be pooled using Rubin’s method. Results from the CMH analysis will be combined using the Wilson-Hilferty transformation as described in the Bohdana Ratitch, et al. paper¹⁰ to produce a pooled CMH test p-value.

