9.2.4 Subgroup Analysis of the Key Secondary Efficacy Endpoints CCI [REDACTED]

Summaries for the key secondary endpoints (without imputation of missing data) will be repeated in the subgroups defined in section [4.9](#).

The main analysis for the key secondary efficacy endpoint will be repeated in the subgroups defined in section [4.9](#). The strata-adjusted difference in proportions of responders with 97.5% CI, pooled CMH test p-value will be derived as described in section [9.1.1](#).

MI will not be repeated on each subgroup and missing values will be imputed using the values of MI under MAR assumption on the ITT Set (dichotomous endpoints will be calculated from the underlying imputed variable).

Forest plots with the result of primary analysis and all subgroup analysis of the key secondary efficacy endpoints will be presented.

CCI [REDACTED]
CI [REDACTED]

[REDACTED]

[figure not shown]
[REDACTED]

[REDACTED]

[REDACTED]

[REDACTED]

CCI

Subjects who took rescue therapies or discontinued treatment due to lack of efficacy or AE/death related to study drug will be considered as treatment failures, and all scores after the intake of rescue therapies or treatment discontinuation due to lack of efficacy or AE/death related to study drug will be assigned the worst possible value. In the case of treatment discontinuation for any other reason, a treatment policy strategy will be used and observed after discontinuation data (if available) will be used.

These continuous endpoints will be analyzed using an ANCOVA with treatment group and analysis center as factors and baseline score as covariate. Missing data will be imputed using MI under MAR assumption (see [Appendix C](#) for details about Multiple Imputation).

CCI

Time to onset of effect on pruritus from baseline (defined as the day when the weekly average of WI NRS shows a change from baseline ≥ 4) will be analyzed using Kaplan-Meier survival functions that will be compared between treatment groups by using the log-rank test. The number and proportion of events and censoring, point estimates of the median, Q1 and Q3 with the corresponding 97.5% CI will be presented and Kaplan-Meier curves will also be provided.

The following censoring rules will be applied:

- Subjects who took rescue therapy before achieving onset of effect on pruritus from baseline will be censored and the date of decision to put subject under rescue therapies will be used as censoring date.

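### Subgroup forest plots reuse center strata pooled on the ITT Set, so small categories lose subjects to zero Mantel-Haenszel weights; coarser strata are a cheap, minor improvement

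*SAP*

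**What the plan says.** For the primary endpoint, SAP 9.1.4 states "The primary analysis for the primary efficacy endpoint will be repeated in the subgroups defined in section 4.9" and adds "The strata-adjusted difference in proportions of responders with 97.5% CI, pooled CMH test p-value will be derived as described in section 9.1.1". On display it says "A Forest plot with the result of primary analysis and all subgroup analysis of primary efficacy endpoint will be presented". For the key secondary endpoints, SAP 9.2.4 says "The main analysis for the key secondary efficacy endpoint will be repeated in the subgroups defined in section" 4.9, with the same derivation and its own forest plots.

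SAP 9.1.1 is a CMH test stratified by analysis center. The risk difference comes from the "large sample approximation method for binary data using Mantel-Haenszel strata weights", with the Sato variance.

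SAP 4.5 sets the strata: "A small center is defined as a center which randomizes less than 15 subjects". Pooling runs within country or geographic region. On the population used, it says "The process of combining centers will be based on the ITT Set, and same pooling will be repeated for the mITT Set". Per-protocol analyses reuse that pooling as well. Subgroups are not mentioned.

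The Protocol Synopsis gives the spread of sites: "Approximately 70 study sites are planned in North America and Europe".

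On weight, protocol 8.6 says the 60 mg arm will help decide whether heavier subjects need weight-based dosing. Protocol 19.6 and SAP 15 name body weight in dose selection, and redacted text follows in both. The subgroup lists in SAP 4.9 and protocol 19.11 have eight factors, and weight is not one of them.

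**The concern.** The strata are built to hold at least 15 subjects over three arms, about five per arm. Within a subgroup category the same strata hold only a fraction of that. Many then contain one arm of a dose-placebo comparison but not the other, and such strata add nothing to the Mantel-Haenszel estimate or to the CMH statistic. The forest plot would show a row for the category while an unknown part of its subjects contributes nothing.

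At stake are the width, and in very small categories the existence, of some exploratory forest-plot rows. A small category would look less informative than its data allow. The separate subgroup summaries do not replace those rows. They leave missing data unimputed, and Appendix F titles them observed case, which SAP section 9 defines as taking post-rescue data as observed. They therefore do not match Estimand 1.

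**Working it through.** **Plan's own figures.** The documents give no figure for subjects lost in subgroups. The related sample-size statement (SAP 4.2) does reproduce: 84 per arm, 20% against 50%, two-sided alpha 0.025 gives 97.3% power, consistent with the stated floor of 90%.

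**Inputs from the documents.** 252 subjects, 84 per arm, 1:1:1 (SAP 4.2, 4.3); about 70 sites, so 252/70 = 3.6 per site; minimum stratum size 15 (SAP 4.5), so at most 252/15 = 16.8, that is 16 strata. The protocol's threshold is 12, but protocol section 19 lets the SAP prevail.

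**Assumed.** Category share s (not stated anywhere); two regions with a 60/40 split of sites; site sizes from even to very uneven; permuted blocks of 3 within site; category membership independent of center unless noted.

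**Mechanism.** In stratum k of a category, with n1 subjects on one dose and n0 on placebo, the Mantel-Haenszel weight is n1 × n0/(n1 + n0). If either count is zero, the weight is zero. This depends on arm, category and stratum, not on the outcome, so multiple imputation does not change it.

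**Closed form.** With K equal strata, a category member is lost when no opposite-arm member shares the stratum, with probability about (1 − s)^(84/K). Simulating the pooling rule gave 11.4 to 14.3 strata on average.

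| Share s | K = 11.4 | K = 14.3 | K = 16 | Simulated loss, uneven sites |
|---|---|---|---|---|
| 5% | 69% | 74% | 76% | 70-76% |
| 10% | 46% | 54% | 58% | 46-57% |
| 25% | 12% | 18% | 22% | 13-22% |
| 50% | 0.6% | 1.7% | 2.6% | 1-3% |

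Example: 0.9^(84/16) = 0.9^5.25 = 0.575. In the full ITT Set (s = 1) the loss is essentially nil.

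**No estimate at all.** With equal strata the chance is [1 − (1 − (1 − s)^(84/K))²]^K. At s = 5% and K = 16: (1 − 0.236²)^16 = 0.40. At K = 10: (1 − 0.350²)^10 = 0.27. Simulation with uneven sites gave 0.30 to 0.36.

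**Confidence intervals.** The unstratified 97.5% half-width at 20% against 50% is 2.2414 × √(0.41/n), with n per arm. The widening factor is 1/√(relative Mantel-Haenszel information).

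| Share | n per arm | Unstratified | Relative information | Factor | Center-stratified |
|---|---|---|---|---|---|
| 10% | 8.4 | ±50 points | 0.436-0.522 | 1.38-1.51 | ±68 to ±75 |
| 25% | 21 | ±31 | 0.731-0.790 | 1.13-1.17 | ±35 to ±37 |
| 50% | 42 | ±22 | 0.898-0.926 | 1.04-1.06 | ±23 to ±24 |

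**Sensitivity.** If membership clusters by center (assumed intraclass correlation 0.05 to 0.20), the loss is 31-47% at 10% and 15-18% at 25%. The simulation pooled within region; pooling first within 4 to 8 assumed European countries moved the share kept by at most about 4 points.

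**With region-only strata.** 95-98% of subjects are kept at a 10% share and over 99% at 20%.

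**The case against.** The strongest reply is that it hardly matters. A 10% category has about 8 subjects per arm, and ±50 points is no more interpretable than ±70. No document gives a category size; four levels of age or race prove only that the smallest holds at most 25%. Keeping the primary estimator in every row also makes the subgroup rows directly comparable with the overall row, and randomization is stratified by site. Most of this stands. It caps the importance of the point and is why the overall estimate should be shown both ways. It does not justify rows that are blank or needlessly wide when coarser strata would avoid that at little cost.

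Redaction also limits the claim. SAP 4.6 is blacked out and Appendices B and C cannot be read, so a sparse-category rule may exist there. SAP 9.1.4 itself points only to 9.1.1.

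A reader might infer three stronger things that the documents do not support:

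- That all the forest plots are compromised. They are not: half-size categories lose 1-3%, and the Region factor loses little because pooling runs within country or geographic region.
- That the primary result or error control is at risk. The subgroup analyses are outside the testing hierarchy of SAP 4.4, and the full ITT Set loses essentially no one.
- That the plan omits an efficacy analysis by weight. The redacted text in protocol 19.6 and SAP 15 sits exactly where one would belong, so this can only be a query.

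**Conclusion.** The point holds as a minor one. Read as written, SAP 9.1.4 and 9.2.4 apply center strata sized for the whole trial to every subgroup category, with no visible re-pooling or fallback. The cost is precision, and in very small categories estimability: roughly half of the subjects in a 10% category, about 13-22% at 25%, 1-3% at one half, and no estimate in roughly 25-40% of trials at 5%. These figures rest on assumed site sizes and category shares; clustering of a category within centers reduces the loss in the smallest ones. The rows likely to be affected are small ones, such as the smallest age, race or duration levels. The displays are exploratory, and the primary test and alpha are unaffected.

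On weight, the visible text supports only this: the factor behind the 60 mg arm in protocol 8.6 is not in the visible subgroup lists. Whether it is analysed elsewhere cannot be judged from the public documents.

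**What to change.** In SAP 9.1.4 and 9.2.4:

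- Estimate subgroup risk differences on the same imputed data, stratified only by the geographic region used for pooling in SAP 4.5, and unstratified for the Region subgroup. Define that region in the text, since the US/Excl-US split of SAP 4.9 need not be the same grouping.
- Print the number of subjects contributing to each row and mark categories that cannot be estimated.
- Show the overall estimate both ways on each forest plot. The downside of the change is that subgroup rows no longer share the center adjustment of the primary analysis, and this makes the difference visible.
- If SAP 4.6 or Appendix B or C already holds a rule for sparse categories, cite it in these sections instead.

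Query to the sponsor: does the redacted text in protocol 19.6 or SAP 15 specify an efficacy analysis by baseline weight? If so, cross-refer to it from SAP 4.9 and protocol 19.11. If not, add a descriptive baseline-weight subgroup at Week 12. Week 4 cannot separate the doses, because both active arms receive the same Day 1 dose (protocol Table 3). With a median split, each half has about 42 per arm, and the 97.5% half-width is ±22 points even unstratified, so the result can only be descriptive.

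Cost: SAP wording, one changed stratification variable in the subgroup programs and one added count per row. If weight is added, a few further tables; baseline weight is already collected (SAP 7.1). No alpha is spent and no new data are needed.
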